6.3. Prohibited Prior or Concomitant Therapy

At screening, the Investigator or delegate will review prior medications use and record all prior medication taken by the subject within 7 days before the screening (or within 14 days before the screening for all antimicrobial agents, and within 30 days before the screening for any other investigational treatment).

UPH-STD-05-01 Version: 0

Effective Date: 06/23/2023 Page **18** of **44**

Patients with current or chronic use (as defined as medication taken daily for \geq 30 days or used on an "as needed" basis for \geq 6 months) of any antibiotics for any clinical indications, other than UTI, will be excluded from the study. Patients will be excluded from the study if they have received any dose of a potentially therapeutic oral or systemic antibiotics for the treatment of UTI within 48 hours before the study baseline urine is obtained.

6.4. Procedure and Consequence for Subject Withdrawal from Study

Removal by Investigator:

The removal of a study patient by the Investigator will be based on the Clinical and Protocol Violation conditions outlined below. Criteria for patient removal at the Investigator's discretion are:

Clinical

A patient may be withdrawn from the study if, in the opinion of the Investigator, it is not in the best interest of the patient to continue. Patients who experience an adverse event (AE) or severe adverse event (SAE) will be assessed by the Investigator to determine disposition.

Protocol Violation

Protocol violations will be assessed by the Investigator on a case-by-case basis to determine subject disposition.

Patients can be withdrawn from the study by the Investigator at any time, or upon request from the Sponsor and with mutual agreement between sponsor and Investigator. The Investigator and/or delegate must inform the patient and/or Sponsor of the removal and provide a rationale.

7. STUDY TREATMENTS

7.1. Subject Enrollment

Each site will recruit and screen approximately 168 adults to identify the defined study population (n=120) based on an assumed 40% screen failure rate.

Patients will have their eligibility assessed by the Investigator and/or delegate, through the review of relevant medical history and other assessments as defined in the protocol.

7.2. Testing Site Setting

The testing sites shall be high-complexity testing laboratories within clinical practices.

UPH-STD-05-01 Version: 0

Effective Date: 06/23/2023 Page **19** of **44**

Doc Lab Inc. / Protocol Number 22-UPHUV-01 Advarra IRB Approved Version 0, Date: 12 May 2023 / Pro00071764

7.3. Study Arms

Active Comparator A

Diagnosis by Molecular Testing, and Treatment based on the results of Urine PCR testing – EVEN numbers on randomization table.

Active Comparator B

Diagnosis by Conventional Testing, and Treatment based on results of the Urine C & S testing – ODD numbers on randomization table.

7.4. Randomization

Enrolled patients will be randomized for one of two testing procedures used to guide treatment. Upon eligibility confirmation, patients will be assigned a unique sequential enrollment/randomization number. Patients with an odd enrollment number will receive treatment guided by urine C&S results, and patients with an even enrollment number will receive treatment guided by urine PCR results.

Enrollment numbers will only be used once. If a patient withdraws from participation in the study, then their enrollment number cannot be reused. Enrollment numbers will be assigned strictly sequentially as potential patients become eligible for randomization.

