Study Arms	 Active Comparator A: Diagnosis by Molecular Testing - Treatment based on the results of Urine PCR testing – even numbers on randomization table. KingFisher Duo Prime QuantStudio 6 and 7 Flex Real-Time PCR System QuantStudio 12k Flex Real-Time PCR System
	Active Comparator B: Diagnosis by Conventional Testing - Treatment based on the results of Urine C & S testing – odd numbers on randomization table
Statistical	Tables, listings and figures (TLFs) will be utilized to summarize data
Methodology	associated with endpoints; discussion sections will be based on

Effective Date: 06/23/2023 Page 11 of 44

observations of this summarized data, with reference to existing literature where appropriate.

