5. STUDY DESIGN

5.1. General Design

This is a multi-center, randomized, parallel-assignment, open-label, clinical utility study to evaluate urine PCR cUTI testing by comparing the diagnostic and therapeutic outcomes of molecular diagnostic methods to those of traditional urine C&S in management of cUTI in adults. At least six (6) sites will participate in this study. Approximately 120 eligible volunteers will be enrolled per site. The study is designed to be a 28-day study, which includes sample collection, sample test, treatment, and follow-up. Patients who meet all of the inclusion criteria and none of the exclusion criteria and sign an informed consent form will be enrolled in the study. During the visit, each enrolled patient will provide a urine sample (at least 8 mL) at V1 and V3; The collected urine specimens will be analyzed using both PCR and C&S methods at

UPH-STD-05-01 Version: 0

[figure not shown]
Effective Date: 06/23/2023 Page **15** of **44**

each timepoint. Upon eligibility confirmation by treating Investigator(s), patients will be randomized in a 1:1 ratio as follows:

- Diagnosis and treatment based on the results of the urine PCR
- Diagnosis and treatment based on the results of the urine C&S

Table 1. Schedule of Assessments summarizes the study procedures to be performed at each study visit. Individual study procedures are described in detail below (see section 8). It may be required to perform outlined procedures at unscheduled time points, if deemed clinically necessary by the Investigator(s). Additional evaluation/testing may be deemed necessary by the Investigator(s) for reasons related to subject safety.

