6. SUBJECT SELECTION AND WITHDRAWAL

6.1. Inclusion Criteria

Subjects must meet all of the following criteria to be considered eligible for admission to the study:

- I1. At least 18 years of age at the time of consent;
- I2. Presenting at least two of the following new, persistent or worsening cUTI signs and symptoms at screening visit:
 - a) fever (temperature >38 degrees Celsius or >100.4 degrees Fahrenheit), hypothermia (temperature <35.5 degrees Celsius or <95.9 degrees Fahrenheit), rigors, or chills
 - b) dysuria, urinary frequency, urgency, or hematuria
 - c) suprapubic pain or pelvic pain
 - d) costovertebral angle (CVA) tenderness
 - e) nausea or vomiting
 - f) radiographic evidence of pyelonephritis
 - g) leukocytosis
- I3. Urine specimen with evidence of pyuria
 - a) dipstick analysis positive for nitrite and/or leukocyte esterase, or;
 - b) \geq 10 white blood cells (WBCs) per cubic millimeter [mm3], or;
 - c) \geq 10 WBCs per high power field (hpf), or;
 - d) clinically suspected pyuria (e.g. change in urine color, sediment in urine, or foul-smelling urine)

UPH-STD-05-01 Version: 0

Effective Date: 06/23/2023 Page 17 of 44

Doc Lab Inc. / Protocol Number 22-UPHUV-01 Advarra IRB Approved Version 0, Date: 12 May 2023 / Pro00071764

- I4. Having cUTI that requires microbiological diagnosis and treatment as suspected by the Investigator;
- I5. Presenting active UTI that failed to resolve on first-line therapy or identified as a high-risk* patient population;
 - *High-risk patient population include those who are elderly (≥65years), male, pregnant, having recurrent UTI (≥3/year), with underlying co-morbidities (e.g. diabetes, immunosuppression, or CKD), or with known functional and anatomical abnormalities of the urinary tract (e.g. stones, stents, recent instrumentation, indwelling catheters, neurogenic bladder, or PKD)
- I6. Able to provide at least 8 mL urine at visit 1 and 3;
- I7. Willing to abstain from sexual intercourse or use condoms during any sexual contact until the EOS visit is complete;
- I8. Willing to comply with protocol requirements, including availability for follow-up for the duration of the study.

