6.2. Exclusion Criteria

Subjects meeting any of the following criteria will not be eligible for admission to the study:

- E1. Unable or unwilling to provide written informed consent;
- E2. Unable to read and write in English (surveys are not available or validated in any other language than English);
- E3. Currently participating in, or has participated in an interventional clinical trial with an investigational product or device within 30 days prior to the Screening Visit;
- E4. Currently on or chronic use of any antibiotics for any clinical indication, other than UTI (refer to section 6.3.);
- E5. Receipt of any dose of a potentially therapeutic oral or systemic antibiotics for the treatment of UTI within 48 hours before the study baseline urine is obtained
- E6. Pregnant women with known fetal congenital anomaly (e.g., genetic abnormality or major congenital malformation) based on antenatal ultrasound;
- E7. Any rapidly progressing disease or immediately life-threatening illness, including acute hepatic failure, or respiratory failure;
- E8. Medical condition or other factor that in the judgment of the investigator might affect ability to comply with procedures.

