8.2. Visit 1 - Screening and Baseline (Day 0)

The delegated study staff will explain the study objectives, the process, and the modalities of participation in the research. The study staff will answer any questions the patient may have. Patients will then be given ample time to review the Informed Consent Form (ICF) and, ask any questions before signing the appropriate section(s). The ICF will then be signed by the Investigator or delegate. A copy of the Informed Consent Form (ICF) will be provided to the patient for their records. The informed consent process will be documented in the source documents.

Once the ICF is signed by the patient and attested to by the Investigators or delegate, the study staff will collect demographic information, vital signs and relevant medical history, and conduct an examination in order to verify the eligibility criteria (excluding urine analysis results).

If the patients meet the inclusion criteria and none of the exclusion criteria (excluding urine analysis results), urine specimens will be collected using acceptable methods (refer to section 9.1). The collected urine specimens will be analyzed by both urine PCR and C&S in accordance with SOPs.

Prior to Visit 2 and upon confirmation of eligibility by an Investigator, patients will be enrolled into the study and will be randomized into one of two study arms (PCR-arm or C&S-arm).

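### Section 7.4 sets the arm by the parity of a strictly sequential number, which is alternation rather than randomization, and nothing conceals the next assignment

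*Combined protocol and SAP*

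**What the plan says.** Section 7.4 (Randomization) uses one number for both enrollment and randomization. The arm follows from it: "Patients with an odd enrollment number will receive treatment guided by urine C&S results", and even numbers go to the PCR arm. On the order of issue it says "Enrollment numbers will be assigned strictly sequentially as potential patients become eligible for randomization". A number is never reused, so a withdrawal does not disturb the odd/even pattern.

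The synopsis (2.1) and Section 7.3 word the mapping slightly differently, as "odd numbers on randomization table" for C&S and "EVEN numbers on randomization table" for PCR. Neither says how that table is produced, whether its entries are in random order, or who holds it.

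On timing, Section 5.1 says "Upon eligibility confirmation by treating Investigator(s), patients will be randomized in a 1:1 ratio as follows", and Section 8.2 likewise says that "upon confirmation of eligibility by an Investigator, patients will be enrolled into the study and will be randomized". So an investigator's eligibility decision comes before allocation. Section 5.1 also describes the study as open-label. The blinding in Section 7.5 covers only the result of the unassigned test, not the allocation.

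**The concern.** Random allocation with concealment does two jobs. It makes the arms comparable apart from chance, and it stops the person enrolling a patient from knowing which arm comes next. The rule in 7.4 does neither.

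The route for bias is concrete, because some entry criteria leave room for judgment. I4 reads "Having cUTI that requires microbiological diagnosis and treatment as suspected by the Investigator"; I3d accepts pyuria on clinical suspicion; E8 excludes for "Medical condition or other factor that in the judgment of the investigator might affect ability to comply with procedures". Staff who can foresee the arm could, without intending to, influence who is declared eligible and in what order patients are entered.

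The primary analysis in 11.3.3 is an unadjusted one-sided Fisher test, so any difference in case mix passes straight into the comparison. Baseline data and the exploratory strata in 11.3.5 could reveal or partly adjust for measured imbalance, but not for the unmeasured part. At stake is the causal reading of the primary result. The 1:1 balance and the ability to compute the test are not affected.

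**Working it through.** **1. What the allocation rule produces.** The inputs, all from 7.4, are consecutive integers, no reuse, odd = C&S and even = PCR. Numbers 1, 2, 3, 4 therefore give C&S, PCR, C&S, PCR. No step is random.

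**2. Whether the table rescues it.** The synopsis and 7.3 could be read as meaning a table of random numbers whose parity sets the arm. Section 7.4, however, makes the enrollment and randomization number the same number and says it is sequential, and a running number is not a random draw. The three places conflict at best, and a site that follows 7.4 will alternate.

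**3. How predictable the next arm is.** The documents do not say whether numbering is per site or study-wide, or who issues it.

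- Per-site numbering, or a visible running number: 100%.
- Study-wide numbering, six equally recruiting sites (assumption), each seeing only its own assignments: the gap between a site's consecutive patients is geometric with p = 1/6. Guessing the opposite of the site's last arm is right when the gap is odd. P(odd gap) = p / [1 − (1 − p)²] = 1 / (2 − p) = 1 / (2 − 1/6) = 6/11 = 54.5%. Simulation also gives 0.545.
- Reference values: simple randomization 50%; permuted blocks at 120 per site, guessing the arm that is behind, simulated at about 68% for mixed blocks of 4/6/8 and about 71% for fixed blocks of 4.

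**4. Reproducing the plan's own figure.** Section 11.1 uses a one-tailed Fisher exact test, 0.70 versus 0.80, α = 0.05, 287 per arm. Power is the sum, over all pairs of binomial outcomes (n = 287 each) that the test rejects, of the product of their probabilities. The result is 0.8513193, as stated. The exact α at a common rate of 0.80 is 0.04044, also as stated (0.0404397).

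**5. Illustration of what a case-mix shift would do.** The size and direction of s are assumptions; the documents give neither. Without a true effect, the arms are set at 0.75 ± s/2. With a true effect, the difference is narrowed by s, split equally between the arms. The second power column is shown because the text of 11.1 assumes 75% for C&S while its software input is 70%.

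| Shift s (points) | Rejection rate, no true effect, favoring PCR | Rejection rate, no true effect, favoring C&S | Power, 70% vs 80%, shift favoring C&S | Power, 75% vs 85%, shift favoring C&S |
|---|---|---|---|---|
| 0 | 0.0412 | 0.0412 | 0.8513 | 0.8980 |
| 1 | 0.0721 | 0.0221 | 0.7768 | 0.8325 |
| 2 | 0.1182 | 0.0110 | 0.6851 | 0.7453 |
| 3 | 0.1822 | 0.0051 | 0.5804 | 0.6392 |
| 5 | 0.3620 | 0.0009 | 0.3620 | 0.4024 |

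The two values of 0.3620 are the same calculation (72.5% versus 77.5%) and are not separate evidence.

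**6. How much steering a shift needs.** Suppose patients of better and worse prognosis differ by 15 to 30 points in favorable outcome (assumption). The share of better-prognosis patients must then differ between arms by s divided by that gap. For s = 1, that is 1/30 to 1/15, or about 3 to 7 percentage points. For s = 5, it is 5/30 to 5/15, or about 17 to 33. The 5-point row is therefore an extreme case.

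**The case against.** The strongest reply is that alternation is one reading and not an established fact. The synopsis and 7.3 refer to a randomization table, so a random list may have been intended, and the study schematic in 5.2 is not available to check. This stands as far as intent goes: what sites will actually do cannot be known from the text. It does not rescue 7.4, which states a complete deterministic rule, and no section describes a random order.

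The second reply is that the error rates come from assumed shifts. That is correct. The larger shifts need substantial steering, and in a measured factor such an imbalance would probably show. The case for change rests on the design defect and not on those percentages.

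The third is that site-stratified blocks of 4/6/8, guessable about 68% of the time, are more predictable than study-wide alternation seen only locally, at 54.5%. This is also correct and bears on the choice of scheme. The 54.5% holds only if the running number stays hidden from sites, which nothing in the documents ensures; whoever issues the number knows the next arm with certainty.

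Lastly, Table 1 marks eligibility again at Visit 2, and 8.3 removes patients negative on both tests after allocation. Concealing the assignment does not close that route. It is a separate matter.

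**Conclusion.** The concern holds and should be corrected before the trial relies on this allocation. As written, 7.4 prescribes alternation in an open-label trial described as randomized, and no section provides a random sequence or concealment. Selection bias is possible; nothing here shows that it has occurred.

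The next arm is known with certainty under per-site or visible numbering. The 54.5% figure assumes study-wide numbering, six equally recruiting sites and no sight of other sites' assignments. The effect on the primary test cannot be sized from the documents. If case mix shifted by 1 to 3 points, the one-sided false-positive rate would be 7.2% to 18.2% instead of 4.1% (shift favoring PCR), or power at the inputs of 11.1 would be 77.7% to 58.0% instead of 85.1% (shift favoring C&S). The loss of concealment cannot be fully repaired in the analysis.

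**What to change.** Replace the parity rule in the synopsis, 7.3 and 7.4 with one consistent description covering:

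- a computer-generated random 1:1 sequence, with the method of generation and the holder of the list named;
- release of each assignment only after eligibility has been confirmed and recorded;
- enrollment numbers kept as identifiers with no link to arm.

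The type of sequence is a choice. Randomly varying permuted blocks stratified by site, with block sizes undisclosed, keep the arms balanced within site but stay partly guessable by someone tracking past assignments (about 68% for 4/6/8). Simple central randomization brings guessing down to 50% but gives up exact balance: at 720 patients the difference in arm sizes has a standard deviation of √720 ≈ 27.

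The list could sit in the EDC or CTMS. Section 16 makes such a system optional and describes it for storing laboratory reports and patient documents, so an allocation function would have to be confirmed. Name a fallback: a central office independent of the sites, or sequentially numbered opaque sealed envelopes.

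The cost is a protocol amendment plus a list, a module or envelopes. Sample size and visits do not change. If a random list already exists, it is enough to describe it, state how it is concealed and correct 7.4 to match.

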7.5. Blinding and Unblinding

The treating Investigator will only have access to the results of their patients' assigned test, and will be blinded to the result of the comparator test until after the end of the study.

The treating Investigator shall gain an access to the result of comparator test in following cases:

- If a patient's assigned test result comes back negative UTI.
- If a patient is withdrawn from the study. In the opinion of the Investigator, it is not in the best interest of the patient to continue study therapy and/or lack of efficacy.
- If patient decide to discontinue study participation.

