UTI treatment and management affects healthcare costs and consumes vast resources in both ambulatory and inpatient settings. Outpatient management for UTIs is becoming limited due to the rising number of antimicrobial resistant cases. As a result of predisposing risks that alter normal urinary tract (functionally or anatomically), cUTI is associated with increased risk of recurrent infection. Furthermore, the management of cUTI starts with the use of empiric broadspectrum antimicrobial therapy that sufficiently covers the most commonly isolated uropathogens. In clinical practice, the choice of antibiotics is determined based on urine culture and antimicrobial sensitivity results. However, urine culture and sensitivity is a time-consuming procedure, where the turnaround time of the results is at least 48 hours, and this delay in a definitive diagnosis of cUTI and identification of infecting microorganisms often results in longer use of empiric broad-spectrum antimicrobial agents. An increased antimicrobial resistance in uropathogens underlying cUTI is attributed to an increased risk of recurrent infection, relapse, and exposure to multiple courses of antimicrobials, which can further complicate treatment course, prolong hospital stays, and lead to high mortality rates. The use of molecular testing for the diagnosis of UTI/cUTI, such as polymerase chain reaction (PCR), can facilitate the detection

UPH-STD-05-01 Version: 0

Effective Date: 06/23/2023 Page 13 of 44

of urinary pathogens with increased sensitivity and rapid turnaround times – that is typically less than 24 hours – and will enable the targeted administration of antimicrobial agents.

The proposed comparator PCR test has completed performance and clinical validation tests where it identified 15 bacterial genus and species, 4 fungal species, 5 STI-causing microorganisms, and 16 different classes of resistance genes. The study reported that all positive samples were identified via PCR at a rate of >90%, indicating that PCR may be more accurate, specific, and sensitive than culture. The clinical utilization of PCR-based diagnosis of UTI/cUTI would be extremely beneficial in ensuring timely treatment by rapid identification of infecting microorganisms and resistance, and eliminating empirical treatment by enabling early targeted treatment, ultimately reducing UTI-related morbidities and costs in a high-risk patient population.

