9. ASSESSMENTS AND PROCEDURES

9.1. Urine Sample Analysis

Urine samples (at least 8 mL) will be collected from a clean-catch mid-stream urine specimen at V1 and V3. Patients will be instructed to follow the clean catch instructions provided at the collection site. The Investigator or delegate may collect the urine samples using a properly disinfected collection techniques such as through a newly-placed urinary catheter, cystoscopy, or suprapubic aspiration, as per clinical indication (See Appendix II for further procedural guidance). Additional urine sample collection and analysis may be conducted at an unscheduled visit, if deemed necessary by treating Investigator. Specimens must be immediately refrigerated upon collection and submitted to the central laboratory within 24 hours of collection. Specimen must be stored and maintained at 2-8 °C when transporting. If transportation to the central laboratory is expected to exceed 24 hours, whole cups of urine specimen must be frozen.

Obtained urine samples will be labelled with subject ID, DOB, visit number, study ID, method of collection, date and time of collection. The collected sample will be placed in a small bag along with the test requisition form. The processing laboratory will aliquot the sample upon receipt, one to be analyzed by PCR (maximum 3mL) and the other to be analyzed by C&S (minimum 5mL). The sample will be stored under the appropriate temperature conditions until analysis of the sample.

Urine C&S

All urine samples for Urine C&S will be shipped to the central laboratory. Urine culture, isolation of uropathogen(s), initial identification of pathogen(s) and bacterial counts in urine will be conducted in the central laboratory.

Urine samples will be cultured and quantified using a calibrated loop to identify a quantitative count of bacteria at a lower limit of 10⁵ CFU/mL. All purified pathogen(s) will be further analyzed for species identification and antimicrobial susceptibility. The analysis results will be recorded in the source document and eCRF.

Urine PCR

Urine samples will be analyzed using the listed molecular testing devices:

• KingFisher Duo Prime

UPH-STD-05-01 Version: 0

Effective Date: 06/23/2023 Page 23 of 44

Doc Lab Inc. / Protocol Number 22-UPHUV-01 Advarra IRB Approved Version 0, Date: 12 May 2023 / Pro00071764

- QuantStudio 6 and 7 Flex Real-Time PCR System
- QuantStudio 12k Flex Real-Time PCR System

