Bacterial and fungal pathogen-directed qualitative PCR amplification of target region of 24 uropathogens, and 16 different classes of resistance genes (see Appendix III. Device specification: pathogen targets and Cq ranges, antibiotics resistance genes and Cq ranges).

Further details of the standardized SOP for PCR procedure will be distributed from a central laboratory to all laboratory sites prior to the commencement of the study.

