Appendix II. Urine Sample Collection

- Early morning urine specimens ('first void specimen') are preferred, however routine or random samples are acceptable.
- Upon sample collection, immediately refrigerate the specimen and submit to the central laboratory within 24 hours of collection (maintain at 2-8 °C when transporting).
- If transportation to the central laboratory is expected to exceed 24 hours, whole cups of urine specimen must be frozen. However, for expedited PCR test processing, aliquot 1mL of urine into two* separate 1.5mL Non-Stick RNase-Free microfuge tubes labeled with patient information. Aliquoted tubes (for PCR testing) and the remaining urine specimen in the cup (for C&S testing) must be place in the freezer (< -20°C).

UPH-STD-05-01 Version: 0

Effective Date: 06/23/2023 Page **39** of **44**

*One tube is for immediate processing on the following work day and the other is a backup in case testing needs to be repeated.

Methods	Supplies	Instruction
Clean-	- Sterile 90 mL container	Patient instructions:
catch	- Towelette	Step 1. Wash and dry your hands thoroughly.
Midstream		Step 2. Remove the container lid and set it aside. Do not touch inner surfaces.
		Step 3. Cleanse your urogenital area ("lower parts") with the towelette provided.
		Women: Wipe from front to back between the folds of skin.
		Continue to hold the skin fold apart until the urine sample is
		collected
		Men: Wipe the tip of the penis (if un-circumcised, retract the foreskin).
		Continue to hold the foreskin back until the urine sample is collected
		Step 4. Pass a small amount of urine into the toilet bowl.
		Step 5. Urinate into the container until the container is 1/2 to 2/3 full
		Step 6. Finish urinating into the toilet bowl.
		Step 7. Replace the lid and tighten firmly.
		Step 8. Wash and dry your hands thoroughly.

Note: The collector must NOT combine urine collected from separate voids to create one specimen of sufficient volume, under any circumstances.

Appendix III. Device specification: pathogen targets and Cq ranges, antibiotics resistance genes and Cq ranges

Pathogen targets	Cq ranges for pathogen detection
 Candida albicans, glabrata, parapsilosis, tropicalis 	
Chlamydia trachomatis	Critically High : 10.000 – 21.000
Citrobacter freundii/braakii	High : 22.000 – 26.000
Citrobacter koseri	Medium : 27.000 – 28.000
Enterococcus faecium, faecalis	Low : 29.000 – 32.000
Escherichia coli	Negative : 40.000 – 33.000;
Gardnerella vaginalis	09.000 - 1.000

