Klebsiella pneumoniae/oxytoca	
Mycoplasma genitalium	
Neisseria gonorrhoeae	
 Proteus mirabilis, vulgaris 	
Pseudomonas aeruginosa	
Serratia marcescens	
• Staphylococcus (coagulase negative: epidermidis,	
haemolyticus, lugdunensis, saprophyticus)	
Staphylococcus aureus	
Staphylococcus saprophyticus	

UPH-STD-05-01 Version: 0

Effective Date: 06/23/2023 Page **40** of **44**

Streptoccoccus agalactia (group B)	
Streptococcus pyogenes	
Trichomonas vaginalis	
Ureaplasma urealyticum	
Acinetobacter baumannii	
Antibiotic resistance genes	Cq ranges for resistance gene
• Class A β-lactamase; blaKPC	identification
• Class A β-lactamase; CTX-M-Group1	
 Class B metallo-β-lactamase; blaNDM 	Positive : 10.000 – 31.000
Class D oxacillinase OXA-48	Negative : 32.000 – 40.000;
Class D oxacillinase OXA51	1.000 - 9.000
• dfr (A1, A5), sul (1,2) probes (Sulfamethoxazole and	
trimethoprim)	
• ermB, C; mefA	
• IMP, NDM, VIM Groups (Carbapenem)	
MRSA* Mec-A	
• PER-1/VEB-1/GES-1 Groups (ESBL)	
• qnrA1, A2	
• qnrB	
• qnrS	
• tetB, tetM	
• VanA, VanB (Vancomycin)	
ACT, MIR, FOX, ACC Groups (Beta Lactams)	

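### Section 7.5 has no release rule for a culture-positive C&S-arm patient who stays in the study and whose baseline PCR detects an STI organism; the treating investigator may not see that result for about 19 to 34 days

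*Combined protocol and SAP*

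**What the plan says.** **Both tests are run on everyone.** Section 8.2 states: "The collected urine specimens will be analyzed by both urine PCR and C&S in accordance with SOPs". This applies in both arms.

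**The PCR panel includes STI organisms.** Section 3 says the validated test identified "15 bacterial genus and species, 4 fungal species, 5 STI-causing microorganisms". Section 9.1 describes the study assay as "Bacterial and fungal pathogen-directed qualitative PCR amplification of target region of 24 uropathogens". Appendix III lists "Chlamydia trachomatis" and "Neisseria gonorrhoeae" among the targets, together with Mycoplasma genitalium, Trichomonas vaginalis and Ureaplasma urealyticum.

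**The unassigned result is masked.** Under section 7.5 the treating investigator "will be blinded to the result of the comparator test until after the end of the study". The result is released in three cases only: the assigned test is negative, the patient is withdrawn, or the patient chooses to discontinue.

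**Neighbouring sections.** Section 8.3 bars review of the unassigned result ahead of treatment, with a negative assigned test as the one exception. Section 8.4 has the investigator complete a questionnaire on both tests at End of Study (Day 28 ± 7). Section 5.3.2 defines end of study for each subject.

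**Timing.** Section 3 gives a PCR turnaround "that is typically less than 24 hours". Section 9.1 requires specimens to be "submitted to the central laboratory within 24 hours of collection".

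**The concern.** The trial itself generates an STI result for each C&S-arm patient, and 7.5 then keeps it from the treating clinician. If the culture is positive and the patient stays in, no visible rule requires anyone to pass on a positive finding before the End-of-Study visit. PCR-arm investigators see the same targets in their assigned report, so the gap falls on one arm.

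What is at stake is patient safety: a treatable infection known to the laboratory could wait three to five weeks. Inclusion criterion I7 (abstinence or condoms until End of Study) limits onward transmission but does not shorten the patient's own delay. Pregnant patients are eligible and are among those the protocol classes as higher risk.

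**Working it through.** The plan states no figure for this delay, so there is none to reproduce. It has to be derived.

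**1. Are the STI organisms part of the study assay?** The section 3 counts give 15 + 4 + 5 = 24 targets, which equals the 24 in section 9.1. Appendix III names all five STI organisms. They are on the panel.

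**2. Does any release case apply?** Take a C&S-arm patient with a positive culture who stays in the study.
- Assigned test negative: no.
- Withdrawn: no.
- Patient discontinues: no.
- Section 8.3 exception: no, because it also needs a negative assigned test.

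**3. How long is the delay?** Delay = End-of-Study day minus the day the baseline PCR result is ready.
- Visit window: 28 − 7 = Day 21; 28 + 7 = Day 35.
- Result on Day 1 (under 24 hours from collection): 21 − 1 = 20 to 35 − 1 = 34 days.
- Result on Day 2 (up to 24 hours in transport, then up to 24 hours of testing): 21 − 2 = 19 to 35 − 2 = 33 days.
- Combined: 19 to 34 days.

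Sensitivity to the assumptions:

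| Assumption | Delay (days) |
|---|---|
| Result on Day 0 | 21 to 35 |
| Result on Day 3 (for example, a frozen specimen) | 18 to 32 |
| Result on Day 1 or 2, seen only 2 to 3 days after Visit 3 | 21 to 37 |

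**4. How many patients?** The documents give neither an STI rate nor a culture-positive rate, so only a per-percent figure is possible.
- Retained per arm, from section 11.1: 720/2 × (1 − 0.25) = 270, or 574/2 = 287.
- Each 1% with both findings: 0.01 × 270 = 2.7 to 0.01 × 287 = 2.9, about 3 patients.
- At 5% (assumption): 13.5 to 14.4 patients.

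These are illustrations and not upper bounds. The rate already requires a positive culture and the base is already net of planned losses, so nothing further comes off.

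**5. What could a release do to the comparison?** If a fraction f of the C&S arm is released and every one of those outcomes changes, that arm's favorable rate moves by f.
- f = 1%: at most 1 percentage point.
- f = 5% (assumption): at most 5 points, half of the 10-point difference planned in section 11.1.

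**The case against.** **The rule may sit elsewhere.** Section 9.1 refers to a PCR SOP that is not in the documents, and the consent form is not visible. Either could cover incidental STI findings. This stands: what is shown is that 7.5 and the rest of the visible protocol give no rule, not that the trial has none.

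**Other routes exist.** The patient can be withdrawn, including at the sponsor's request (6.4) or for lack of efficacy (7.5). An abnormal test can be handled as an adverse event (10.1.1), staff can recall the patient (10.5), and PCR can be repeated at an unscheduled visit (Table 1, note e). A reader might infer from 7.5 that nobody can act before End of Study; these routes show that goes too far. But each is discretionary, or needs continuing symptoms or someone who has seen the result, and no such person is named. The remaining gap is mainly the patient whose symptoms settle on culture-guided treatment.

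**Section 8.3 is narrower than 7.5.** It bars review only ahead of treatment. True, but it grants no later access, while 7.5 expressly continues the masking. The questionnaire text in 8.4 follows the End-of-Study urine sampling and may mean those results, so it is weak evidence of when the baseline PCR is first seen.

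**Culture alone would not have found the organism.** A reader might infer that C&S-arm patients receive substandard care. The documents do not show a shortfall in culture-guided care. The point is that the study creates a result and has no visible rule for passing it on.

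**Release weakens the contrast.** STI detection is part of what PCR-guided care offers, so giving it to control investigators removes some of the difference under test. This stands and is a real cost of the fix.

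**Conclusion.** The concern holds as a gap in the visible protocol. Section 7.5 keeps the treating investigator masked, and no release case reaches a culture-positive C&S-arm patient who stays in. Unless a discretionary route is used, a positive STI result can go unreported to that investigator for about 19 to 34 days.

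The range assumes a PCR result on Day 1 or 2 and release at the patient's own Visit 3, consistent with 5.3.2. Reading the end of the study in 7.5 as the end of the whole trial would lengthen it. The number of patients is unknown, at about 3 per 1% of the retained arm with both findings.

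A reader might also infer bias in the primary endpoint. The documents do not support that: nothing in them links the withheld STI result to a shift in favorable outcome in either direction. This is a change the sponsor should make on safety grounds, held with medium confidence because the SOP and consent form cannot be seen.

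**What to change.** Add a fourth release condition to 7.5: when the baseline PCR of a patient assigned to C&S is positive for C. trachomatis, N. gonorrhoeae or T. vaginalis, the laboratory reports those targets alone to the site within 24 hours of the result. The interval mirrors the 24-hour rule for Visit 2 in 8.3. Uropathogen and resistance-gene results stay masked, and care stays with the treating investigator. The same sentence should say whether M. genitalium and U. urealyticum are in or out. Record the release and any treatment on the eCRF. If an SOP already covers this, cite it in 7.5 instead.

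Report the number released. As a supportive analysis only, repeat the 11.3.3 test excluding patients in both arms who are baseline-positive for exactly the released organisms. Both arms have baseline PCR, so the same criterion applies to each. The result describes the effect in patients without those organisms; it does not recover the uncontaminated contrast in the full population.

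**Cost.** One condition, one short laboratory report, one eCRF field and one extra run, or a single cross-reference. The downside is that some control-arm investigators receive a small part of the PCR information. STI treatment could then affect the cUTI outcome or, if parenteral, the parenteral-avoidance component in 11.3.2, within the bound of 1 point per 1% of the arm released.
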